2.2 Objectives of the study

2.2.1 Primary objective

The primary objective is to describe the characteristics of mRCC patients achieving a CR with Sunitinib (Cases) and compare them to the characteristics of mRCC patients not achieving a CR with Sunitinib (Controls) to identify factors associated with the occurrence of CR.

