2.5 Number of patients required

The primary objective of the study is to describe the characteristics of mRCC patients achieving a CR with Sunitinib (Cases) and to compare them to the characteristics of metastatic renal cell carcinoma patients not achieving a CR with Sunitinib to identify factors associated with the occurrence of complete remission.

A sample size of N = 40 cases and N = 80 controls will provide a power of 80% in the detection:

- For continuous variable with a normal distribution, of an effect size (Cohen's d) ≥ 0.55 ;
- For a dichotomous variable, of a frequency difference between cases and controls corresponding to the ORs presented in the table below:

Frequency in controls	10%	20%	30%	40%	50%	60%	70%	80%	90%
Odds Ratio	≥ 4.33	≥ 3.27	≤ 0.19 or ≥ 3.16	≤ 0.26 or ≥ 3.12	≤ 0.29 or ≥ 3.44	≤ 0.32 or ≥ 3.78	≤ 0.32 or ≥ 5.29	≤ 0.31	≤ 0.23

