4 GENERAL CONSIDERATIONS FOR THE STATISTICAL ANALYSIS OF THE DATA

4.1 Statistical methods

The biostatistics department at AXIAL will perform the statistical analysis, with the exception of the analysis of biological data and biomarkers. Data will be analysed using SAS® software (version 9.4 or later - SAS Institute, North Carolina, USA).

Statistical tests will be carried out bilaterally at a 5% significance level (alpha).

Results will be presented in the form of tables per group (Cases/Controls) presenting:

- For quantitative parameters: number of patients (n), mean and standard deviation, minima and maxima, median and quartiles, and number of missing values.
- For qualitative parameters: number of patients, absolute and relative frequencies for each parameter modality, and number of missing values. Missing data will not be considered when calculating percentages.

Quantitative parameters will be compared between groups using the following methods: Beforehand, the distribution of the parameter will be checked graphically and by using Skewness and Kurtosis and Shapiro-Wilk statistics. If the distribution is considered normal, groups will be compared using a Student's t-test and the difference in means and the 95% Confidence Interval (CI) will be presented. If this is not the case, groups will be compared using a Wilcoxon rank sum test and Hodges-Lehmann estimator, with a presentation of the 95% CI.

For non-ordinal qualitative variables, groups will be compared using the Chi-2 test (or Fisher's exact test if the theoretical numbers <5) and the odds ratio will be presented when specified.

For ordinal qualitative variables, groups will be compared using the Cochran-Mantel-Haenszel test, ridit modified scores ('row mean score differ'). For ordinal qualitative count variables, groups will be compared using the Cochran-Mantel-Haenszel test, 'row mean score differ' table option.

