6.3.2 Other characteristics

Study population: Population of patients included

The demographic characteristics of the patients will be described by group and compared:

- Time of diagnosis of metastatic renal cell carcinoma;
- Nephrectomy (Yes/ No)*;
If Nephrectomy:
 - Extended or partial;
 - With or without adrenalectomy;
 - With or without curettage;
 - Open or laparoscopic approach;
 - Time between diagnosis of metastatic renal cell carcinoma to nephrectomy (in months);

- Pathological classification (Clear cell carcinoma / Papillary carcinoma / Chromophobe carcinoma / Bellini duct carcinoma / Medullary carcinoma / Sarcomatoid carcinoma / Other);
A list of other classifications will be presented.
- TNM classification (T / N / M and TNM);
- Tumour size (mm);
- Furhamn nuclear grade (I / II / III / IV);
- Necrosis (Yes/ No)*;
- Pulmonary embolism (Yes/No)*;
- Sarcomatoid component (Yes/No)*.

** For these qualitative variables, the odds ratio (Case versus Control) will be presented.*

The demographic characteristics of the patients, at initiation of Sunitinib, will be described by group and compared:

- Time between diagnosis of metastatic renal cell carcinoma and initiation of Sunitinib (in months);
- Location of metastases:
 - Lung (Yes/ No);
 - Bones (Yes/No);
 - Liver (Yes/ No);
 - Adrenal glands (Yes/No);
 - Pancreas (Yes/No);
 - Brain (Yes/No);
 - Lymph nodes (Yes/No);
If Lymph nodes:
 - Supra-diaphragmatic (Yes/No);
 - Sub-diaphragmatic (Yes/No);
 - Recurrence at nephrectomy site (Yes/No) ;
 - Other (Yes/ No);
A list of the other locations will be presented.
- Number of metastatic sites;
- MSKCC prognostic classification (Good prognosis/Intermediate prognosis/Poor prognosis).

The characteristics of the patients in CR will be described for the Cases:

- Time between Sunitinib initiation and CR (years);
- Method of achieving the CR (Medical treatment alone/Combined with local treatment);
If combined:
 - Surgery (Yes/No);
 - Radiotherapy (Yes/ No);
 - Radiofrequency (Yes/ No);
 - Cryoablation (Yes/ No);
 - Metastasectomy (Yes/ No);
 - Other (Yes/ No);

A list will be presented of local treatments including dates of treatment, time between the diagnosis of metastatic renal cell carcinoma and local treatment and sites exposed.

- Radiological assessment of the CR:
 - Disappearance of all known target lesions (Yes/No);
 - Disappearance of all non-target lesions (Yes/No);
 - No new lesions (Yes/No);

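### SAP 6.3.2 appears to test supra- and sub-diaphragmatic nodes only in node-positive patients, which is not the site-versus-CR comparison that the primary objective asks for

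*SAP*

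**What the plan says.** The primary objective is to compare Cases with Controls "to identify factors associated with the occurrence of CR" (SAP 2.2.1). The sample-size section claims 80% power for 40 Cases and 80 Controls in the detection "of a frequency difference between cases and controls corresponding to the ORs presented in the table below" (SAP 2.5).

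SAP 6.3.2 names the included patients as its population and lists characteristics at Sunitinib initiation for description and comparison by group. Lung, bone, liver, adrenal glands, pancreas, brain and lymph nodes are each Yes/No items. Below lymph nodes, after "If Lymph nodes", come the supra-diaphragmatic and sub-diaphragmatic Yes/No items. The same layout is used earlier in the section for the details of a nephrectomy.

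SAP 4.1 compares Yes/No items by chi-square, or by Fisher's exact test when expected counts fall below 5, two-sided at 5%. It adds: "Missing data will not be considered when calculating percentages". SAP 5.1 allows no replacement of missing values outside listed cases, and none of these concerns nodal sites. No derivation in SAP 5.2 sets the two sub-sites to No for a patient without node metastases.

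**The concern.** A nephrectomy type is undefined in a patient who had no nephrectomy, so conditioning is unavoidable there. A nodal site is different. A patient without node metastases is a known No at both sites, and removing that patient discards information.

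Once node-negative patients are removed, the quantity compared is the share of node-positive patients who have the site. That share depends on how common the other nodal site is. Two misreadings become possible:

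- A site equally frequent in Cases and Controls can look associated with CR because the other site differs.
- A site that does differ can look unassociated because the other site differs in the same direction.

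The effective sample also falls below the 40 and 80 on which the power statement rests. Two candidate factors under the primary objective are affected.

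**Working it through.** **1. The plan's own figure.** Inputs from SAP 2.5 and 4.1: 40 Cases, 80 Controls, two-sided 5%, 80% power. Using the pooled two-proportion z formula and moving the Case frequency in steps of 1/40 until power reaches 80%, all 14 tabulated odds ratios are reproduced. Example at a Control frequency of 30% and OR 0.19: Control odds are 0.30/0.70 = 0.429; 0.429 × 0.19 = 0.081; Case frequency is 0.081/1.081 = 7.5%, that is 3/40. Power is 84% by the formula and 86% by exact enumeration of the chi-square test. The table is therefore right, provided that all 40 + 80 patients enter the test.

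**2. What the restricted test compares.** Let s and u be the supra- and sub-diaphragmatic frequencies, taken as independent within a patient. Node-positive frequency is 1 − (1 − s)(1 − u), and the share with supra-diaphragmatic nodes given nodes is s / [1 − (1 − s)(1 − u)].

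- Supra equal at 30%, sub 10% in Cases and 30% in Controls. Cases: 0.30/0.37 = 81%. Controls: 0.30/0.51 = 59%. The odds ratio in all patients is 1. Among node-positives it is (0.30/0.07)/(0.30/0.21) = 3.0. Expected node-positives: 14.8 Cases and 40.8 Controls.
- Both sites at OR 0.19, so 7.5% and 30%. Cases: 0.075/0.144 = 52%. Controls: 59%. Expected node-positive Cases: 40 × 0.144 = 5.8. A large site difference has almost vanished.

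**3. Rejection rates for the supra-diaphragmatic item.** Simulation of 40 Cases and 80 Controls under the SAP test rule. All site frequencies are assumptions.

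| Supra, Cases/Controls | Sub, Cases/Controls | Node-positives only | All patients | Parent lymph-node test |
|---|---|---|---|---|
| 30/30% | 30/30% | 5% | 5% | 5% |
| 30/30% | 10/30% | 31% | 5% | 29% |
| 30/30% | 15/30% | 17% | 5% | 18% |
| 20/20% | 5/20% | 25% | 5% | 26% |
| 7.5/30% (OR 0.19) | 30/30% | 69% | 86% | 36% |
| 7.5/30% (OR 0.19) | 20/20% | 57% | 86% | 49% |
| 7.5/30% (OR 0.19) | 7.5/30% | 3% | 86% | 99% |
| 57.5/30% (OR 3.16) | 30/30% | 54% | 83% | 52% |
| 57.5/30% (OR 3.16) | 57.5/30% | 17% | 83% | 94% |

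**4. Count examples under the same rule.**

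- Supra-diaphragmatic nodes in 10/40 Cases and 20/80 Controls, with 12 and 48 node-positive. All patients: OR 1.0, p = 1.00. Node-positives, 10/12 against 20/48: OR (10 × 28)/(2 × 20) = 7.0, p = 0.0098.
- 6/40 against 29/80, with 10 and 48 node-positive. All patients: OR (6 × 51)/(34 × 29) = 0.31, p = 0.016. Node-positives, 6/10 against 29/48: OR (6 × 19)/(4 × 29) = 0.98, p = 1.00.

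The parent lymph-node test gives p = 0.0019 and p = 0.0003 respectively.

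**5. Loss of sample alone.** Take the plan's entry at a Control frequency of 50%, "≤ 0.29 or ≥ 3.44". At OR 3.44 the full design has about 85% power. If the same odds ratio holds within node-positive patients and the same fraction of both groups is node-positive, the z formula gives:

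| Node-positive fraction | Patients tested | Power at OR 3.44 | OR detectable with 80% power |
|---|---|---|---|
| 30% | 12 + 24 | 34% | 14.6 |
| 40% | 16 + 32 | 44% | 8.0 |
| 50% | 20 + 40 | 54% | 5.9 |
| 60% | 24 + 48 | 62% | 4.8 |
| 80% | 32 + 64 | 75% | 3.7 |

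**The case against.** **The denominator is inferred.** The SAP never says that the sub-site tests are confined to node-positive patients, and the indented line could be mere table layout. The CRFs (Protocol Appendices 5 and 6) give each sub-site its own Yes/No boxes without a skip instruction. A recorded No is not missing, so the missing-data rule would not remove it. Protocol 8.8 compares all collected variables and states no nodal restriction. All of this stands. If node-negative patients are coded No and kept, the problem disappears. But nothing in the SAP says so, and the parallel with the nephrectomy items points the other way.

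**The restricted test is not a faulty test.** A reader might infer an inflated type I error. The documents do not support that: the test keeps its 5% level for its own null, equal split among node-positive patients. The fault is that this null is not the association sought.

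**The parent item is tested in all patients.** A reader might infer that a nodal association would be missed altogether. When both sites shift together, the lymph-node test rejects in 94% to 99% of the simulated trials, so the association is seen and only its location is lost. The protection is partial: when only one site differs at OR 0.19, the parent test rejects in 36% to 49%, against 86% for the all-patient sub-site test.

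**The sizes are assumed.** This stands. With a latent correlation of 0.5 between the sites, the 31% falls to 27% and the 25% to 18%.

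**Little rests on these two items.** They are two among many unadjusted comparisons, and SAP 6.3.2 promises no odds ratio for any location. This stands and sets the weight.

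**Conclusion.** The point holds as a minor one. On the natural reading of SAP 6.3.2, two comparisons under the primary objective answer a conditional question instead of the one asked, and the power stated in SAP 2.5 does not apply to them. Under the assumed prevalences, rejection with equal site frequencies reaches 17% to 31% instead of 5%. Power at OR 0.19 is 57% to 69% instead of 86%, and about 3% when both sites share the effect. If the other site has the same frequency in both groups and there is no association, the restricted test behaves correctly.

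The conclusion rests on three things: the inferred denominator, the assumed site frequencies, and independence of the two sites within a patient in the simulation.

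The documents do not support reading this as an error in the sample-size table, which reproduces for 40 and 80. Nor do they support extending it to SAP 6.4 and 6.5. Those sections describe one group at a time without a Case-Control test, and percentages among node-positive patients are acceptable there.

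**What to change.** In SAP 6.3.2, add one sentence: each nodal sub-site will be compared between groups in all included patients, with patients without node metastases counted as No for both; the split among node-positive patients will be described without a p-value. Lymph-node status that is itself unknown should stay missing.

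No change is needed in SAP 6.4 or 6.5. The cost is that sentence and one derivation rule. No new data are required, because both CRFs already record lymph nodes and each sub-site as Yes/No.

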Because complete remission is a rare event, one can stipulate that this situation should be a model for studying the pathology of mRCC in response to Sunitinib. It should also permit the sensitivity and resistance to Sunitinib to be explored.

Research is also required to identify markers that can facilitate the screening of patients who would be at low risk of recurrence after complete remission and could potentially benefit from a discontinuation of treatment.

To this end, it is essential to explore the characteristics of the patient at the time of the complete remission compared to those observed at the time of the recurrence, if this occurs, in order to attempt to answer the following questions:

- Is it possible to identify a differential blood marker at the time of the CR compared to the recurrence phase?
- Does one have to distinguish between a CR obtained with medical treatment only and one obtained with the combination of "medical treatment + localized treatment" when, during the retrospective analysis of a series of cases, the 2 cohorts presented the same time to recurrence?
- Can we identify serum or histologic biomarkers that are potentially predictive of a recurrence or CR?
- Is there a correlation between biomarkers identified in patients in CR with Sunitinib compared to patients not in CR with Sunitinib?
- Does the identification of biomarkers help physicians make the decision to stop or continue treatment after obtaining a complete response under sunitinib?

Several biomarkers belonging to different categories, are undergoing investigation because they could reflect the emergence of a resistance or sensitivity to the medicinal product:

- Adhesion molecules (cadherin-6, E-cadherin, MUC1/EMA, ICAM-1, VCAM-1, ELAM- 1, KSA)
- Inducers of immunosuppression (HLA class 1, IL-6, IL-8, IP-10, MIG, MIP1b, B7-H1, B7-H4, CD44)
- Growth factor receptors (VEGFR-3, TGFbR-II, FGFR)
- Hypoxia-inducible factors (CAIX, CAXII, CXCR-4, HIF-1a, VEGF, IGF-I)
- Proliferation markers (Ki-67, PCNA, Ag-NORs)
- Cell cycle regulatory proteins (p53, Bcl-2, PTEN, cyclin A, Akt, p27)
- Analysis of single nucleotide polymorphisms (SNPs) of VEGF and of VEGFRs
- Others (VHL, mTOR, ribosomal protein S6, survivin, IMP3, caveolin-1, PCR, vimentin, fascin, serum amyloid A, NGAL, IGF-1).

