Some of these biomarkers can be detected in the serum (SDF1a, IL-6, IL-8, bFGF, sICAM1, LDH, VEGF, PIGF, soluble VEGF receptors, collagen IV, CPCs, SNPs of VEGF)¹⁶ and will be explored in the context of CR, especially IL-8, which has been the most documented¹⁷.

Other potential biomarkers expressed on the surface of tumor cells or immune cells can be investigated by immunohistochemistry such as:

- The expression of BAP1, SETD2, PBRM1, as well as PD1 or PDL1
- Potential biomarkers of inflammation and lymphocyte infiltrate

A classification according to the tumor expression profile will be performed (B. Beuselinck et al, CCR, 2015).

In addition, we will be able to carry out the sequencing of the most frequently mutated genes (PBRM1, BAP1, VHL)

Because, at present, circulating tumor cells can only be studied in fresh blood, and because this marker has not yet been validated as regards mRCC, this investigation will not be possible with our cohort. However, circulating free DNA is currently being investigated as a substitute for circulating tumor cells in various tumor models (prostate, colon and breast) and we regard it as a good candidate for study in our population at the time of CR compared to recurrence, if it occurs.

Therefore, the aims of this multicenter prospective study on patients with metastatic renal cell carcinoma in CR with Sunitinib with or without associated localized treatment and control patients with metastatic renal cell carcinoma treated with Sunitinib are:

- a) To analyze the characteristics of patients with mRCC in CR with Sunitinib
- b) To assess the possibility of patients in CR to discontinue Sunitinib
- c) To collect a prospective bank of blood samples in order to study blood biomarkers in the context of the CR and during recurrence
- d) to collect a bank of histological specimens to study biomarkers before the initiation of sunitinib;
- e) To assess the correlation between biomarkers analyzed in patients in CR and patients not in CR with Sunitinib

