2.2.2 Secondary objective(s)

The secondary objectives are to:

- Describe the therapeutic management (discontinuation or continuation of systemic treatment in CR patients);
- Search for and describe various biomarkers in a histological sample bank when initiating Sunitinib in CR patients (Cases) and non-CR patients taking Sunitinib (Controls);
- Search for and describe various biomarkers in a histology specimen bank for CR patients with Sunitinib (Cases) and at the time of recurrence, if any;
- Compare the identified biomarkers of CR patients (Cases) with those of non-CR patients taking Sunitinib during the 36 months of the study (Controls).

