If the day is missing, it will be replaced by the first day of the month.
If the month is missing, only the year will be used.*
- Time between CR and progression (in months):
(Date of progression - Date of CR) / 365.25 x 12
*Note: In case of incomplete dates (date of CR or date of progression):
If the day is missing, it will be replaced by the first day of the month.*
- Progression-free survival (in months):
It is defined as the time between CR and progression or death.
(Date of the event - Date of CR) / 365.25 x 12
Note: Patients who have not progressed and who have not died will be censored at the date of last visit.

Event	Censor decision	Date of the event or censor
Progression	Non-censored	Date of progression
All-cause death without progression	Non-censored	Date of death
Lost to follow-up	Censored	Date of last visit
End of study without progression or death	Censored	Date of last news

For Controls:

- Time between initiation of treatment and progression (in months):
(Date of progression - Date of treatment initiation) / 365.25 x 12
*Note: In case of incomplete dates (date of treatment initiation or date of progression):
If the day is missing, it will be replaced by the first day of the month.*
- Progression-free survival (in months):
It is defined as the time between treatment initiation and progression or death.
(Date of the event - Date of treatment initiation) / 365.25 x 12
Note: Patients who have not progressed and who have not died will be censored at the date of last visit.

Event	Censor decision	Date of the event or censor
Progression	Non-censored	Date of progression
All-cause death without progression	Non-censored	Date of death
Lost to follow-up	Censored	Date of last visit
End of study without progression or death	Censored	Date of last news

- Duration of treatment with Sunitinib (in months):
(Date of treatment discontinuation - Date of treatment initiation + 1) / 365.25 x 12
*Note: In case of incomplete dates (initiation date or discontinuation date):
If the day is missing, it will be replaced by the first day of the month.*

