 - All target and non-target lymph nodes <10 mm (Yes/No);
- Therapeutic strategy after CR (Continuation of Sunitinib treatment/Discontinuation of Sunitinib treatment).

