Patient follow-up data will be described for the cases at the end-of-study visit:

- Best objective response observed after progression (Complete / Partial / Progressive / Stabilised);
- Duration of treatment received after progression with first-line Sunitinib (months);
- Early termination of the study (Yes/No);
- Response achieved (persistent CR since inclusion visit / CR after treatment of recurrence / Disease progression);
- Number of subsequent treatment lines from progression, post CR;
- Death (Yes/ No).

Progression-free survival at the end of the study will be analysed using the Kaplan Meier method, with a presentation of the survival curve. The progression-free survival rate will be estimated with a 95% confidence interval.

6.5 Description of follow-up visits for mRCC patients treated with first-line Sunitinib, non CR (Controls)

Study population: Population of followed-up patients - Controls

Patient follow-up data will be described for the controls at 6 and 12 months of treatment:

- Sunitinib dose (50 mg / 37.5 mg / 25 mg);
- Current regimen (4/2 / 2/1 / Continuous);
- Clinical assessment (Complete Response / Partial Response / Stable Disease / Progression);
If Partial Response:
 - Percentage of tumour reduction (%)
- Location of metastases:
 - Lung (Yes/ No);
 - Bones (Yes/No);
 - Liver (Yes/ No);
 - Adrenal glands (Yes/No);
 - Pancreas (Yes/No);
 - Brain (Yes/No);
 - Lymph nodes (Yes / No); If Lymph nodes:
 - Supra-diaphragmatic (Yes/No);

- Sub-diaphragmatic (Yes/No);
- Recurrence at nephrectomy site (Yes/No) ;
- Other (Yes/ No);
A list of the other locations will be presented.
- Number of metastatic sites;

Patient follow-up data will be described for the controls at the time of the progression:

- Time between initiation of treatment and progression (in months);
- Type of progression (Local Progression/Distant Progression);
If distant progression, at which level (at a known metastatic site/new metastatic site);
- Location of metastases:
 - Lung (Yes/ No);
 - Bones (Yes/No);
 - Liver (Yes/ No);
 - Adrenal glands (Yes/No);
 - Pancreas (Yes/No);
 - Brain (Yes/No);
 - Lymph nodes (Yes / No); If Lymph nodes:
 - Supra-diaphragmatic (Yes/No);
 - Sub-diaphragmatic (Yes/No);
 - Recurrence at nephrectomy site (Yes/No) ;
 - Other (Yes/ No);
A list of the other locations will be presented.
- Number of metastatic sites;

Patient follow-up data will be described for the controls at the end-of-study visit:

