Table X - Progression-free survival analysis (months) - Kaplan-Meier

	Total (N=XX)
Progression-free survival (months)	
Number of subjects	99
Event	99 (99.9)
Censored*	99 (99.9)
Min	99.9
Max	99.9
Q3 [95% CI]	99.9 [99.9;99.9]
Median [95% CI]	99.9 [99.9;99.9]
Q1 [95% CI]	99.9 [99.9;99.9]
Mean progression-free survival [95% CI]	99.9 [99.9;99.9]

Name of the SAS programme: P:\XXXXX\XXXXX\Analyse\Pgm\nom_du_programme.sas

Date and time when programme was executed: DDMMYYYY HH:MM

Study: A6181209 - OVERVIEW
Group: XXXXX

Table X – Description of adverse events (AE) by System Organ Class (SOC) and Preferred term (PT)

	Cases (N=XX)		Controls (N=XX)	
	Nb of events	Nb (%) of patients	Nb of events	Nb (%) of patients
At least one adverse event	xx	x (xx.x%)	xx	x (xx.x%)
Body system 1	xx	xx (xx.x%)	xx	xx (xx.x%)
Preferred term 1	xx	xx (xx.x%)	xx	xx (xx.x%)
Preferred term 2	xx	xx (xx.x%)	xx	xx (xx.x%)
...				
Preferred term n	xx	xx (xx.x%)	xx	xx (xx.x%)
Body system 2	xx	xx (xx.x%)	xx	xx (xx.x%)
Preferred term 1	xx	xx (xx.x%)	xx	xx (xx.x%)
Preferred term 2	xx	xx (xx.x%)	xx	xx (xx.x%)
...				
Preferred term n	xx	xx (xx.x%)	xx	xx (xx.x%)
....				
Body system n	xx	xx (xx.x%)	xx	xx (xx.x%)
Preferred term 1	xx	xx (xx.x%)	xx	xx (xx.x%)
Preferred term 2	xx	xx (xx.x%)	xx	xx (xx.x%)
...				
Preferred term n	xx	xx (xx.x%)	xx	xx (xx.x%)

Name of the SAS programme: P:\XXXXX\XXXX\Analyse\Pgm\nom_du_programme.sas

Date and time when programme was executed: DDMMMYYYY HH:MM

Study: A6181209 - OVERVIEW
Group: XXXXX

Table X - Description of adverse events

	Cases (N=XX)	Controls (N=XX)
Qualitative variable		
n	xx	xx
Category 1	xx (xx.x%)	xx (xx.x%)
...
Modality n	xx (xx.x%)	xx (xx.x%)
Missing data	xx	xx
Note: the unit of analysis is the adverse event		

Name of the SAS programme: P:\XXXXX\XXXX\Analyse\Pgm\nom_du_programme.sas
Date and time when programme was executed: DDMMYY HH:MM

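### The protocol aims to assess whether patients in CR can stop Sunitinib, but the SAP reports no outcome by continuation or discontinuation

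*SAP*

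**What the plan says.** The list of aims that closes the rationale in Protocol section 6 includes, as item (b), "To assess the possibility of patients in CR to discontinue Sunitinib". The same section asks whether biomarkers can "help physicians make the decision to stop or continue treatment after obtaining a complete response under sunitinib".

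The formal objective is narrower. SAP 2.2.2 words it as "Describe the therapeutic management (discontinuation or continuation of systemic treatment in CR patients", and Protocol 3.1 and section 7 likewise speak of describing.

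The analyses planned for Cases are:

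- SAP 6.3.2, at inclusion: "Therapeutic strategy after CR (Continuation of Sunitinib treatment/Discontinuation of Sunitinib treatment", as a two-category description.
- SAP 6.4, at 12 and 24 months: ongoing treatment, temporary and permanent stops with reasons, resumption, and durations.
- SAP 6.4, at progression and at end of study: time from CR to progression, duration of additional Sunitinib after CR, Sunitinib restart, and best response after progression.
- SAP 6.4, survival: "Progression-free survival at the end of the study will be analysed using the Kaplan Meier method, with a presentation of the survival curve". SAP 5.2 sets the origin for Cases: "It is defined as the time between CR and progression or death".

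The shell in SAP Annex 1, "Table X - Progression-free survival analysis (months) - Kaplan-Meier", has a single Total column. SAP 2.4 defers only biological data and biomarkers to a separate analysis plan.

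**The concern.** Assessing whether patients in CR can stop treatment requires, at the least, the outcome of those who stopped. The SAP describes who continued and who stopped, and separately describes progression and PFS, but it never crosses the two. The single Case curve averages over both strategies.

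SAP 2.1 gives as background that, in one case series, almost half of discontinuations were followed by recurrence. Following the SAP exactly, this study could not set a figure of its own beside that one, although the strategy recorded at inclusion, progression and death are all collected. A reader would be left to infer the outcome after discontinuation from a mixed group.

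**Working it through.** **1. Is the analysis planned anywhere?** Aim (b) concerns the outcome of a choice. SAP 6.3.2 tabulates the choice. SAP 6.4 tabulates treatment course and progression for all Cases together. The PFS shell has no column by strategy, and the separate plan in SAP 2.4 does not cover this. No PFS, recurrence rate, time to progression or response to restart is planned by continuation versus discontinuation.

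**2. The plan's own sample-size figure.** SAP 2.5 states 80% power for Cohen's d of 0.55 with 40 Cases and 80 Controls, two-sided 5%. The noncentrality is 0.55 × √(40 × 80 / 120) = 2.84. The normal approximation gives Φ(2.84 − 1.96) = 81.1%, and the noncentral t with 118 degrees of freedom gives 80.4%. The figure reproduces, but it concerns Cases versus Controls. The documents give none for a comparison within Cases.

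**3. What pooling hides.** Without censoring, pooled PFS is the weighted mean of the two groups' PFS. As an illustration with equal groups, a pooled 50% is equally compatible with 50% and 50% or with 70% and 30%, since 0.5 × 70 + 0.5 × 30 = 50.

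**4. Precision of an estimate by strategy.** The documents do not give the split, so group sizes are assumed. PFS is taken as 50% without censoring; this value is an assumption too, because the background proportion has no stated time horizon. Half-width = 1.96 × √(0.25 / n):

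| n | Half-width | Wilson 95% interval |
|---|---|---|
| 40 (all Cases) | 15.5 points | 35% to 65% |
| 20 | 21.9 points | 30% to 70% |
| 15 | 25.3 points | not calculated |
| 10 | 31.0 points | 24% to 76% |

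Censoring would widen these intervals.

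**5. Would a test be worthwhile?** By Schoenfeld's formula, the hazard ratio detectable with 80% power is exp[(1.96 + 0.84) / √(D × s × (1 − s))], for D events and a share s in one group. I assume 12, 20 or 28 events among 40 Cases (30%, 50%, 70%):

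| Split | Detectable HR at 12 / 20 / 28 events | Power for HR 2 at 12 / 20 / 28 events | Events needed for HR 2 |
|---|---|---|---|
| 20/20 | 5.04 / 3.50 / 2.88 | 22% / 34% / 45% | 66 |
| 10/30 | 6.47 / 4.25 / 3.40 | 18% / 27% / 36% | 88 |

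Both event requirements exceed the 40 Cases planned. Estimates with intervals are therefore defensible, and a test is not.

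**6. How the split has to be made.** The inclusion criteria allow CR up to 5 years before inclusion, and follow-up runs 3 years from inclusion. A curve from CR without delayed entry would count time in which no included Case could have died. Grouping by whether a patient ever stopped would add two biases: a late stopper must first have remained under observation long enough to stop, and progression is itself a listed reason for stopping in SAP 6.4. Grouping by the strategy recorded at inclusion, and counting follow-up only from inclusion, fixes the group before follow-up begins.

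**The case against.** The strongest reply is that nothing formal is unanswered. Aim (b) stands only in the rationale. The secondary objective is to describe, and SAP 6.3.2 and 6.4 do describe. This stands, and it limits the point to a mismatch between a stated aim and the analysis.

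A reader might infer that the SAP only counts who stopped. The documents do not support this: reasons, number and duration of temporary stops, resumption, and time on Sunitinib since CR are also planned. What is missing is any outcome by strategy.

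A reader might also infer that the strategy is fully dated. It is not. The inclusion item in the Case report form (Protocol Appendix 5) is two yes/no lines without a date, and cessation dates appear only on the annual-visit form. The item records strategy following CR, which need not be treatment status at inclusion. A patient who continued for a time and stopped before inclusion may fit neither category cleanly. A curve by this item is therefore PFS from inclusion given the recorded strategy; it is not PFS from the day of stopping. That limitation is real and belongs in the label.

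Finally, two small non-randomised curves could be over-read. That too stands, and is why the proposal has no test and an explicit label.

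**Conclusion.** The point holds as a gap between Protocol aim (b) and the SAP: no outcome is linked to continuing or stopping after CR. It does not touch the primary objective, and the formal descriptive objective is met. It is an inexpensive improvement to a secondary description.

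Under the assumed 20 or 15 patients per group, 50% PFS and no censoring, each estimate would carry about ±22 or ±25 points; the smaller group of a 10/30 split would carry about ±31. These sizes rest wholly on an assumed split and event rate.

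A stronger inference, that the study could show whether stopping is as good as continuing, is not supported. The choice is not randomised, and even a hazard ratio of 2 would have at most 45% power in the scenarios examined.

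**What to change.** In SAP 6.4, add one descriptive Kaplan-Meier PFS figure with a matching table shell:

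- Population: Cases who are progression-free at inclusion.
- Groups: strategy after CR as recorded at inclusion (continued / discontinued). List separately any patient with both or neither option ticked.
- Time: start at the inclusion visit, or keep CR as origin with delayed entry at inclusion.
- Later changes: keep patients in their inclusion group and report subsequent strategy changes alongside. Do not group by ever-stopped.
- Output: estimates with 95% intervals and no test, labelled non-randomised and confounded by indication.

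The cost is one figure and one shell, with no new data collection. The downside is small groups and confounding, both to be stated in the label. If the sponsor prefers not to add the analysis, aim (b) in Protocol section 6 should be restated as describing practice only, in line with the secondary objective.
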